3.5.3 Safety Set

The SS will include all enrolled study participants who are dosing with commercial CZP per protocol at Screening.

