5.4 Screen failures

Screen failures are defined as participants who consent to participate in the clinical study but are not subsequently entered in the study. A minimal set of screen failure information is required to ensure transparent reporting of screen failure participants to meet the Consolidated Standards of Reporting Trials publishing requirements and to respond to queries from regulatory authorities. Minimal information includes demography, screen failure details, eligibility criteria, and any serious adverse event (SAE).

Individuals who do not meet the criteria for participation in this study (screen failures) may be rescreened; however, a study participant may not be enrolled for consecutive pregnancies. Rescreened participants should be assigned the same participant number as for the initial Screening.

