8.3.5 Pregnancy

Details of the pregnancies for all study participants will be collected from enrollment into the study and up to the SFU. UCB standing guidance for collection of data pertaining to pregnancy and pregnancy outcomes will be used during this study for the collection of such data (Section 8.2.5). Information regarding collection of pregnancy-related data is located in Appendix 4 Section 10.4.

Abnormal pregnancy outcomes (eg, spontaneous abortion, fetal death, stillbirth, congenital anomalies, and ectopic pregnancy) are considered SAEs.

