10.1.3 Informed consent process

Participant's informed consent must be obtained and documented in accordance with local regulations, ICH-GCP requirements, and the ethical principles that have their origin in the principles of the Declaration of Helsinki.

Prior to obtaining informed consent, information should be given in a language and at a level of complexity understandable to the participant in both oral and written form by the investigator (or designee). Each participant will have the opportunity to discuss the study and its alternatives with the investigator.

Prior to participation in the study, the ICF should be signed and personally dated by the participant, or her legal representative, and by the person who conducted the informed consent discussion (investigator or designee). The participant or her legal representative must receive a copy of the signed and dated ICF. As part of the consent process, each participant must consent to direct access to her medical records for study-related monitoring, auditing, IRB/IEC review, and regulatory inspection.

If the ICF is amended during the study, the investigator (or the Sponsor, if applicable) must follow all applicable regulatory requirements pertaining to the approval of the amended ICF by the IRB/IEC and use of the amended form.

All studies conducted at centers in the United States must include the use of a Health Insurance Portability and Accountability Act Authorization form.

The participant may withdraw her consent to participate in the study at any time. A participant is considered as enrolled in the study when she has signed the ICF. An eCRF must not be started, nor may any study specific procedure be performed for a given participant, without having obtained her written consent to participate in the study.

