2.2.1.1 Secondary Outcome variables

- Plasma levels of ADA throughout the study period
- Treatment-emergent adverse events from time of informed consent through Safety Follow-up (SFU)
- Pregnancy outcome

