A predose sample 12 weeks (± 1 week) postpartum will be collected during the Postpartum Period. If possible, 1 additional postdose sample 1 week (± 1 day) after the 12 weeks postpartum dose will also be collected.

• **Safety Follow-up contact:**

All study participants will be contacted via telephone for a SFU 5 weeks (± 5 days) after final study visit.

If any participant withdraws early, she will complete the SFU contact.

The end of the study is defined as the date of the SFU/last contact of the last participant in the study.

Number of participants:

Approximately 25 to 30 participants are planned to be screened to achieve approximately 20 enrolled study participants (i.e., study participants who have provided the first blood sample). Enrollment will occur until a minimum of 10 study participants have longitudinal data (defined as at least 4 quantifiable predose and 2 quantifiable postdose PK samples during pregnancy and at least 1 quantifiable postpartum sample) over the study period.

Treatment groups and duration:

[figure not shown]
This study will include pregnant women who have decided to continue treatment with commercial CZP in accordance with their treating physician prior to participating in the study. Study participants will be responsible for obtaining and administering commercially available CZP under the care of their physician and according to the locally approved product label.

The total study duration for a study participant will be a maximum of 53 weeks (40 weeks gestation period and up to 13 weeks (± 3 days) postpartum).

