4.2.1 Handling of missing data for AE

All AEs will be considered TEAEs in this study. For analyses of TEAEs, a complete date must be established to correctly identify the TEAE as occurring during the pregnancy period or not. For purposes of imputing missing components of partially reported start and stop dates for TEAEs, the algorithms listed below will be followed.

Although the algorithms for pregnancy period or not depend on the onset date, imputation rules are provided for stop date as well, as these may be needed for certain statistical analyses, such as an analysis of TEAE prevalence or TEAE duration.

Start and stop dates of TEAEs will be displayed as reported in the study participant data listings (i.e., no imputed values will be displayed in data listings).

Imputation of Partial Start Dates

- If only the month and year are specified and the month and year of study enrolment is not the same as the month and year of TEAE onset, then use the 1st of the month
- If only the month and year are specified and the month and year of study enrolment is the same as the month and year of TEAE onset, then use the date/time of study enrolment

- If only the year is specified, and the year of study enrolment is the same as the year of TEAE onset, then use the date/time of study enrolment
- If the TEAE onset date is completely unknown, then use the date of study enrolment

Imputation of Partial Stop Dates:

- If only the month and year are specified, then use the last day of the month
- If only the year is specified, then use December 31st of that year
- If the imputed stop date is after last contact date, use last contact date.
- If the TEAE is resolved and the stop date is completely unknown, then do not impute the stop date

Other imputation

In addition, the following will apply for presenting TEAE in summary tables:

- if the intensity of an TEAE is unknown, it will be considered as severe.
- If the relationship to CZP is missing, it will be considered as related.

For seriousness, no imputation rule will be applied, the worst-case approach will be applied for the analysis of Serious TEAEs (i.e., the missing seriousness will be considered as serious if missing).

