11 SAFETY ANALYSES

All safety analyses will be performed using the SS.

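### Adverse events count from consent but the Safety Set begins at the Visit 2 blood sample, so a pregnancy loss or disqualifying SAE between the two reaches no safety output

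*SAP*

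**What the plan says.** **Event window.** SAP 2.2.1.1 gives the secondary safety outcome as "Treatment-emergent adverse events from time of informed consent through Safety Follow-up (SFU"). SAP 4.2.1 adds: "All AEs will be considered TEAEs in this study". Protocol 8.3.1 also starts collection at signature of the consent form.

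**Analysis set.** SAP 11 states: "All safety analyses will be performed using the SS". SAP 11.3 uses the same set for the TEAE and serious TEAE listings, and the pregnancy outcome listing (SAP 11.1) falls under the SAP 11 rule. SAP 3.5.3 defines the set: "The SS will include all enrolled study participants who are dosing with commercial CZP per protocol at Screening".

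**Meaning of enrolled.** SAP 2.3 explains enrolled participants as "study participants who have provided the first blood sample", and SAP 3.5.2 requires both the signed consent form and that sample. Protocol 10.1.3 says something different: "A participant is considered as enrolled in the study when she has signed the ICF".

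**Women who consent but do not enrol.** Protocol 5.4 requires some data on them: "Minimal information includes demography, screen failure details, eligibility criteria, and any serious adverse event (SAE"). Protocol 8.3.5 limits collection of pregnancy data: "Details of the pregnancies for all study participants will be collected from enrollment into the study and up to the SFU". SAP 5.1 summarises screen-failure reasons and lists disposition and termination details on the All Study Participants Set (ASPS).

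**The concern.** These women are pregnant and taking CZP when they consent, so the exposed and observed time starts there. Membership of the Safety Set is settled later, by a condition that some of the events of interest make impossible to meet. Time between consent and Visit 2 is then counted only for women whose events in that time did not stop them enrolling. This is conditioning on survival to Visit 2.

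At stake are the early-pregnancy part of the secondary safety objective, the serious TEAE table, the first-trimester part of the TEAE table by trimester, and the pregnancy outcome listing. With about 20 women in the set, one omitted loss changes what a reader sees.

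**Working it through.** The plan has no safety rate, power figure or formula to reproduce. The check traces the definitions and then does arithmetic on the planned flow.

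**Step 1: the route into the Safety Set.**
- A woman consents after pregnancy is confirmed, while on CZP (Protocol 1.1). AE collection begins.
- Eligibility is confirmed again at Visit 2, just before PK sampling, and she must then be pregnant at no more than 10 weeks (Protocol 5.1).
- Exclusions also apply at Visit 2, including significant morbidity in the past 12 weeks and clinically significant pregnancy-related abnormalities (Protocol 5.2).
- The first PK sample is drawn at Visit 2 (Protocol Table 1-1). I take this to be the first blood sample meant in SAP 3.5.2. Only then is she enrolled and able to enter the Safety Set.

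**Step 2: the same event on either side of Visit 2.**
- A spontaneous abortion is always an SAE (Protocol 10.4).
- Just after the first sample, the woman is discontinued (Protocol 7.2), but she is in the set and the event is a serious TEAE.
- Just before it, she cannot be enrolled, so the event is in no table or listing under SAP 11.
- Another SAE before Visit 2 is omitted only if it prevents the sample. If she still enrols, it is counted.

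**Step 3: what remains visible.** SAP 5.1 would show her in the screen-failure reasons and termination details, without SAE or pregnancy-outcome output. If she is later re-screened successfully, SAP 3.5.1 keeps only the successful record, so even that trace leaves the ASPS.

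**Step 4: planned flow (SAP 2.3: 25 to 30 screened, about 20 enrolled).**
- 25 − 20 = 5 unenrolled; 5/25 = 20%.
- 30 − 20 = 10 unenrolled; 10/30 = 33%.
- These cover every reason for not enrolling and are ceilings, not estimates of omitted events.

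**Step 5: sensitivity to an assumed rate.** The documents give neither an event rate before Visit 2 nor a screening-period length. Let p be an assumed probability, per consented woman, of an event that prevents Visit 2. The expected number omitted is N × p, and the chance of at least one is 1 − (1 − p)^N.

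| Assumed p | Expected, N = 25 to 30 | Chance of at least one |
|---|---|---|
| 1% | 0.25 to 0.30 | 22.2% to 26.0% |
| 2% | 0.50 to 0.60 | 39.7% to 45.5% |
| 5% | 1.25 to 1.50 | 72.3% to 78.5% |
| 10% | 2.5 to 3.0 | 92.8% to 95.8% |

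**Step 6: one omitted loss, none later (assumed counts, all consented women on CZP).** The Safety Set shows 0/20 = 0% (95% Clopper-Pearson interval 0 to 16.8%). Among consented women it is 1/25 = 4.0% (0.1 to 20.4%) or 1/30 = 3.3% (0.1 to 17.2%). The intervals overlap almost entirely. The difference that matters is whether the event is shown at all.

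**The case against.** The strongest reply is that such a woman is not lost. Her SAE reaches the sponsor within 24 hours (Protocol 8.3.1), is reviewed continuously (Protocol 8.4) and is kept as screen-failure data. Pregnancies on CZP are also followed through routine pharmacovigilance forms (Protocol 2.3, 10.4). A reader might infer that these events disappear from the trial; the documents do not support that. What stands is narrower: they are missing from the planned safety outputs.

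A second reply is that under Protocol 10.1.3 she is enrolled at consent and so belongs in the Safety Set. SAP 3.9 also describes the updated set as covering all participants with ongoing CZP dosing at screening, without the word enrolled. This shows an unreconciled definition but does not close the gap, because the operative set definitions in SAP 3.5.2 and 3.5.3 govern the analysis. The restriction to enrolled women is also in Protocol 9.1, so the SAP did not create it.

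A third reply concerns size, and much of it stands. The window is short, since Visit 2 must fall by 10 weeks. Many of the 5 to 10 unenrolled women would fail for reasons unrelated to outcome, such as TB results, gestation or dosing history, some of them found at Visit 1. It would be wrong to read all of them as selected on outcome, or to treat step 6 as the bias in a planned estimate: pregnancy outcome is only listed, and no loss rate is planned. The study has a single arm and no formal test, so no treatment comparison is distorted.

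A reader might also conclude that TEAE tables should start at Visit 2. That would depart from the endpoint in Protocol section 3, which runs from consent, and would take non-serious events before Visit 2 out of the tables.

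**Conclusion.** The point holds as a gap in safety reporting. On the SAP's own definitions, a CZP-exposed woman with a pregnancy loss between consent and Visit 2 is in no AE, SAE or pregnancy-outcome output. The same is true of another SAE in that interval when it prevents the Visit 2 sample. Non-disqualifying events from that interval are reported for women who enrol, so the omission depends on outcome.

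Its size is unknown and probably small. It is bounded by the 5 to 10 women planned to be unenrolled for any reason, and the probabilities in the working rest wholly on assumed rates. The conclusion also assumes that SAP 3.5.2, not Protocol 10.1.3, decides who is enrolled. It is a cheap improvement to completeness and does not undermine the study's main PK results.

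**What to change.** - Keep the TEAE window from consent, as the protocol endpoint states.
- Add to SAP 11 one listing of SAEs and known pregnancy losses, from consent onward, for all consented women on CZP who are not in the Safety Set.
- Include in it the failed-screening records of re-screened women, which SAP 3.5.1 drops from the ASPS.
- Cite the listing beside the serious TEAE table and the pregnancy outcome listing.
- Reconcile Protocol 10.1.3 with SAP 3.5.2, and align the wording of SAP 3.9 with SAP 3.5.3.

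The cost is one extra listing and a few lines of text. The SAE data are already required for screen failures. Pregnancy outcomes are less certain: Protocol 8.3.5 starts collection at enrolment and Protocol 5.4 does not name outcome among the minimum data. They can be shown for unenrolled women only where SAE reports or the routine pregnancy forms supply them, and a footnote should say so.

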3.5.4 Pharmacokinetic Per Protocol Set

The Pharmacokinetic Per-Protocol Set (PK-PPS) is a subset of the SS, consisting of those study participants for whom at least one predose or postdose sample is available which was not impacted by an important protocol deviation.

3.6 Treatment assignment and treatment groups

The study will include pregnant women who have decided to continue treatment with commercial CZP in accordance with their treating physician prior to participating in the study. The commercially approved dosing regimens (200mg Q2W or 400mg Q2W or 400mg Q4W) will be permitted following the guidance of each study participant's physician.

After enrolment into the study, the study participant's physician may modify the dosing regimen as necessary. In such cases, non-approved CZP dosing regimens will also be allowed, at the discretion of the study participant's physician and in a manner independent of this study, as long as the regimen does not exceed 400mg Q2W and the dose is recorded in the diary. All dosing regimens outside the commercially approved will be categorized as other.

3.7 Center pooling strategy

No center pooling is planned for this study.

3.8 Coding dictionaries

All medications other than CZP will be classified by WHO Anatomical Therapeutic Chemical (ATC) Classification, presenting Anatomical Main Group (ATC Level 1), Pharmacological Subgroup (ATC level 3), and preferred term, using version MAR/2021 or later of the World Health Organization Drug Dictionary (WHO-DD), according to UCB standard operating procedures. Medical procedures will not be coded.

All adverse events (AEs) will be considered as treatment emergent adverse events (TEAEs) and will be classified by primary system organ class (SOC), high level term (HLT) and preferred term (PT) using MedDRA® version 24.1 or later. UCB Standard Operating Procedures will be followed.

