7.1.1 Temporary discontinuation

If a study participant has at least 1 PK sample obtained during pregnancy and then CZP dosing is interrupted and restarted, or dosing is modified during pregnancy, the study participant will continue to be followed and all samples will be obtained per protocol guidelines (including postpartum samples).

If a study participant has multiple PK samples obtained during pregnancy and discontinues CZP during pregnancy (with the intention to restart CZP after delivery), a PK predose sample will be obtained at 12 weeks (± 1 week) postpartum with a potential postdose sample 1 week (± 1 day) after the predose postpartum sample. If the study participant does not take CZP for at least 12 weeks and provides a PK sample within this window, the study participant will be discontinued from the study.

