8.5 Treatment of overdose

Excessive dosing (beyond that prescribed per the local label) will be recorded by the study participant in the diary and also recorded in the eCRF. The dosing documentation will be reviewed and verified by the investigator and/or home health nurse. Any SAE or nonserious AE associated with excessive dosing must be followed as any other SAE or nonserious AE.

Overdose events are only considered AEs or SAEs if there are associated clinical signs and symptoms or if the act of taking the excess CZP itself is an AE or SAE (eg, suicide attempt).

UCB does not recommend specific treatment for an overdose. In the event of an overdose, the treating physician should:

1. Contact the Medical Monitor immediately.
2. Closely monitor the participant for any AE/SAE and laboratory abnormalities until commercial CZP can no longer be detected systemically (at least 70 days).
3. Obtain a plasma sample for PK analysis within 70 days from the date of the last dose of commercial CZP if requested by the Medical Monitor (determined on a case-by-case basis).
4. Document the quantity of the excess dose as well as the duration of the overdose in the eCRF.

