9.3.3.1 Adverse events

All AEs will be coded using the Medical Dictionary for Regulatory Activities (MedDRA v24.1 or higher) and characterized as treatment-emergent according to the intake of CZP.

The occurrence and incidence of treatment-emergent adverse events (TEAEs) will be summarized by MedDRA system organ class and preferred term. The occurrence and incidence of TEAEs will also be summarized by intensity and by relationship to CZP. Adverse events leading to discontinuation and SAEs will also be summarized.

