3.9 Changes from protocol-defined analyses

The following change from the protocol have been implemented in the SAP:

- The protocol stated the secondary outcome variable of 'adverse events from time of informed consent through Safety Follow-up', this will now be 'Treatment-emergent adverse events from time of informed consent through Safety Follow-up'.
- The protocol defines 'baseline' for plasma concentration data as the predose measurement 12 weeks (± 1 week) postpartum. In the SAP, tables and figures, the name for the reference point was changed to 'postpartum'.

- Clarification was added to the Enrolled Set definition to include participants who re-enrolled. The SS definition was updated to include all participants with ongoing CZP dosing at screening. PK-PPS definition was clarified to include participants for whom at least one predose or postdose sample is available which was not impacted by an important protocol deviation.

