11.3 Adverse events

All AEs will be coded using the Medical Dictionary for Regulatory Activities (MedDRA v24.1 or later version) and characterized as treatment emergent.

The occurrence and incidence of TEAEs will be summarized by MedDRA system organ class and preferred term. The TEAEs will also be summarized by intensity and by relationship to CZP. TEAEs leading to discontinuation and serious TEAEs will also be summarized.

The following TEAE tables will be produced:

- Incidence of TEAEs Overview
- Incidence of TEAEs by SOC, HLT and PT
- Serious TEAEs
- Non-serious TEAEs
- TEAEs leading to death

- TEAEs leading to hospitalization or death
- TEAEs leading to study discontinuation
- Incidence of TEAEs by Maximum Severity
- Incidence of TEAEs by Maximum relationship
- Incidence of TEAEs by Trimester

The following TEAE of interest will be summarized in stand-alone tables:

- Serious infections including opportunistic infections (see Section 11.3.1)
- Malignancies or unspecified tumours including lymphoma
- Malignant Tumours
- Demyelinating-like disorders
- Aplastic anemia, pancytopenia, thrombocytopenia, neutropenia, and leucopenia
- Serious bleeding events

For the following AEs of interest, no additional tables will be provided, as these are included in the standard AE summaries:

- Congestive heart failure
- Lupus and lupus-like syndrome
- Serious skin reactions (e.g., Stevens Johnson Syndrome, toxic epidermal necrosis, and erythema multiforme).

Separate tables will be created to summarize each of the above TEAEs of interest by system organ class, high level term, and PT, where the TEAEs of interest are identified using standardized MedDRA queries (SMQ). An additional review cycle to confirm the targeted events will be implemented for opportunistic infections as described in Section 11.3.1.

All TEAEs and serious TEAEs will be listed using the SS. Details of serious TEAEs, TEAEs leading to death or study discontinuation will be listed. For results disclosure on public registries (e.g., ClinicalTrials.gov), TEAEs and serious TEAEs will be published.

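### The SAP makes every adverse event treatment-emergent, drops the protocol's CZP-intake criterion without declaring it, and plans no table that separates events on CZP from events off CZP

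*SAP*

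**What the plan says.** Protocol 9.3.3.1 says that adverse events are to be "characterized as treatment-emergent according to the intake of CZP". It gives no start rule, end rule or residual window.

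Three current sections of the SAP leave intake out:

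- SAP 3.8: "All adverse events (AEs) will be considered as treatment emergent adverse events (TEAEs").
- SAP 4.2.1: "All AEs will be considered TEAEs in this study". The onset date is used only to decide whether an event fell in the pregnancy period.
- SAP 11.3: "All AEs will be coded using the Medical Dictionary for Regulatory Activities (MedDRA v24.1 or later version) and characterized as treatment emergent". This is the protocol's sentence without its intake clause.

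SAP 3.9, which lists departures from the protocol, changes the name of the secondary outcome: "this will now be 'Treatment-emergent adverse events from time of informed consent through Safety Follow-up". It does not mention that the intake criterion has gone.

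The protocol allows time off drug within follow-up. Sections 4.1 and 7.1.1 keep a woman in the study if dosing is interrupted and restarted, and also if, after multiple PK samples, she "discontinues CZP during pregnancy (with the intention to restart CZP after delivery"). Adverse events are collected from consent to the safety follow-up contact whatever the dosing (protocol 8.3.1).

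**The concern.** A secondary objective is the safety of CZP across the course of pregnancy. A reader of a TEAE table will normally take the label to mean that an exposure test was applied. Here none is: the label is attached to every event, so it carries no information about exposure.

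For a woman who keeps dosing this makes no difference. For a woman who stops mid-pregnancy, a disease flare or obstetric complication months after her last dose appears under her enrollment regimen as treatment-emergent. The overview, trimester, seriousness and relationship tables cannot show that she was off drug. SAP 11.3 also sends TEAEs to public registries under that label. SAP 3.9 does not help, because a change from adverse events to TEAEs reads as a narrowing to exposed events when nothing has been narrowed.

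**Working it through.** The plan states no figure for this point, so there is nothing to reproduce. The check sets the texts side by side and then sizes the possible effect.

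**Does any other SAP rule separate off-drug events?**

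- Safety Set (SAP 3.5.3): depends on CZP dosing at Screening, so a woman who stops later stays in.
- Table column (SAP 3.1): the regimen in effect at enrollment, so she stays in that column.
- Not Dosed column (SAP 3.1): only women with no recorded dose relative to any PK sample before discontinuation. Later stoppers are not covered.
- Relationship table (SAP 11.3): rests on the investigator's causality judgement, not on dosing dates. A missing relationship is imputed as related (SAP 4.2.1).
- Trimester table (SAP 11.3): splits by gestational age, not by intake.

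None applies an intake criterion. The data to apply one exist: the diary records the date and time of each CZP dose (protocol 6.4).

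**How much off-drug time could there be?**

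Inputs from the documents: enrollment by week 10 (inclusion criterion 3), predose samples every 4 weeks, gestation of 40 weeks, up to 13 weeks postpartum, and follow-up contact 5 weeks later.

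Assumptions: enrollment and first sample at week 10, stop right after the k-th predose sample, delivery at week 40, restart at delivery. A restart close to delivery is implied for a woman who stays in, because she needs at least 12 weeks of CZP by a sample due 12 (± 1) weeks postpartum.

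Stop week = 10 + 4(k − 1). Weeks off CZP in pregnancy = 40 − stop week.

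The documents give no residual window for adverse events. Two illustrative values are used: 35 days (5 weeks, borrowed from the follow-up interval) and 70 days (10 weeks, from protocol 8.5, where monitoring after an overdose continues "until commercial CZP can no longer be detected systemically (at least 70 days")).

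| Stops after predose sample | Stop week | Weeks off CZP | Beyond 35 days | Beyond 70 days |
|---|---|---|---|---|
| 2nd | 14 | 26 | 21 | 16 |
| 4th | 22 | 18 | 13 | 8 |
| 6th | 30 | 10 | 5 | 0 |

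Enrolling at week 6 instead adds 4 weeks to each off-drug entry.

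Collection from enrollment to the follow-up contact is about (40 − 10) + 13 + 5 = 48 weeks. For a stop after the second sample, 26/48 = 54% of that time is off CZP, or 16/48 = 33% after a 70-day allowance. Every event in that time is a TEAE under the SAP.

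**What does one woman do to a table?**

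The safety denominator is the Safety Set, planned at about 20 enrolled women. If a woman's only event in a given table falls off drug, she adds 1/20 = 5.0 percentage points to incidence. Three such women add 3/20 = 15 points. In a single-regimen column the step would be larger, but the documents do not give the split by regimen.

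**The case against.** The case for the SAP as it stands is a serious one, and several parts of it hold.

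- **The protocol has no cut-off.** Every participant has at least 12 weeks of CZP behind her at enrollment (inclusion criterion 4), so treating everything from consent onward as emergent is one workable reading. This stands for the start of the window. It does not cover the end, where a criterion based on intake must at least ask whether intake was continuing.
- **The protocol's endpoint is all adverse events from consent to follow-up.** The SAP tables deliver exactly that under another name, and removing events from them would narrow it. This stands, and it is why the complete summaries should stay.
- **Other safeguards exist.** Investigators assess causality with the timing of dosing in mind (protocol 10.3), TEAEs are tabulated by relationship, and every event is listed. With about 20 women a reader could work through the listings. This softens the problem but does not cure it, for the reasons given for the relationship table.
- **The study is small, exploratory and descriptive.** No inference turns on these tables, and inclusion criterion 5 requires that each woman expects to continue CZP. The effect may be nil. This also stands.

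A reader might go further and infer that the SAP counts off-drug events as on-drug events, or charges them to CZP. The SAP never says so; it gives a label and leaves causality to the investigator. A reader might also infer that the protocol sets a 70-day rule that the SAP has abandoned. It does not: 70 days belongs to overdose monitoring and is worded as a minimum, so weeks beyond it cannot be called drug-free with confidence.

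**Conclusion.** Wrong as written, in a limited way. The protocol ties treatment-emergent status to CZP intake, the SAP removes that tie in three places, and SAP 3.9 does not declare it. Followed exactly, the SAP labels events well after a woman's last dose as treatment-emergent, with no on/off-CZP split in any table.

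The size is conditional. Each affected woman is worth about 5 percentage points on about 20 enrolled. It would be tempting to use the 15 evaluable participants and quote 1/15 = 6.7 points, but safety tables are based on the Safety Set, so 20 is the planned denominator. The 5 points also apply only if she has no on-drug event in the same table. The off-drug weeks shown depend on assumed stopping times and residual windows, and run from 16 weeks to none under the 70-day illustration with enrollment at week 10. The documents do not say how many women will stop, so they do not support a claim that the safety results, or the late-trimester results in particular, will in fact be distorted.

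**What to change.** - Keep the full summaries of every event from consent to the follow-up contact, and label them all AEs.
- From diary dosing dates, derive a flag for each event: onset on CZP, or within a prespecified residual window after the last dose, versus onset off CZP. The sponsor should choose and justify the window; 70 days is only an example, taken from the overdose section.
- Show the overview, trimester, serious and relationship summaries split by that flag. Reserve the term TEAE for the intake-based category.
- Amend SAP 3.8, 4.2.1 and 11.3 to match, and declare in SAP 3.9 how the rule departs from, or makes specific, protocol 9.3.3.1.

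The cost is one derived variable from data already collected, a modest amount of extra table programming, and the need to commit to a window. No event is lost from reporting.
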